5.4.4. Rules for breaking the blinding

This study adopts the double-blind method:

Primary disclosure will be performed after completion of the final version of the statistical plan, audit report and database lock. At this stage, the random numbers will be grouped according to the study arm for statistical analysis by group.

Secondary disclosure discloses the drug corresponding to the group code, experimental drug or PLACEBO. Disclosure documents will be signed by the Sponsor and Research Coordinator.

6. TRATAMENT OF PARTICIPANTS

For the purposes of this protocol, AZVUDINE is the investigational drug that will be administered concomitantly with the standard treatment for COVID-19, as per healthcare organizations' guidelines. The investigational drug will be compared to PLACEBO, also administered concomitantly with the standard treatment for COVID-19. When referring to the investigational (AZVUDINE) or control (PLACEBO) product, the term experimental drug or PLACEBO will be used.

6.2. EXPERIMENTAL TRATAMENT

6.2.1. Formulation and appearance

AZVUDINE: The lyophilized formulation of AZVUDINE is a preservative-free, white to yellowish, odorless and tasteless solid containing 1mg of AZVUDINE.

AZVUDINE is supplied as a sterile product in a white, round, wide-mouthed, high-density polyethylene vial with a polypropylene cap. In addition to the active ingredient, the lyophilized formulation of AZVUDINE contains the following inactive

ingredients: microcrystalline cellulose, hydrated lactose, polyvinylpyrrolidone K30, croscarmellose sodium, magnesium stearate.

PLACEBO: The manufacturing and packaging process for PLACEBO is the same as for the investigational drug, conducted by the same manufacturer and production line. The freeze-dried PLACEBO formulation provided is identical in physical appearance to the active freeze-dried formulation and contains the same inactive ingredients and will be used in the study for masking purposes.

6.2.2. Packaging and labeling

The investigational drug and PLACEBO will be shipped by the sponsor to the research center in white, round, wide-mouthed, high-density polyethylene vials with the country-specific label and polypropylene caps.

AZVUDINE tablets 1mg / PLACEBO 35 tablets /battle FOR CLINICAL RESEARCH ONLY Internal Use / Prescription according to Research Protocol SEARCH CODE: IGZ-1 Producer: "Beijing Union Pharmaceutical Factory" China. Address:[name]. ORPC/CRO: Galzu Institute for Research, Teaching, Science and Applied Technology. Name of the Principal Investigator: [name]. Lot number: _______ Date of manufacture: ______ Patient randomization number ______ Feep out of reach of children Maintain at room temperature Validity: 2 years

Figure 6: Clinical research drug label

Investigational products will be received by the center in separate boxes of AZVUDINE and PLACEBO, with serial number "X to Y" for AZVUDINE and serial number "Z to W" for PLACEBO, for example. There will be a label for participant identification during dispensing, which will be done by double checking.

Each bottle with 35 individual tablets will have a label with the information in Figure 1manufacturer's name and address, lot number, medication identification number, participant information, care statement, instructions for use and dosage (mg), expiration date, storage conditions, and an indication of "For clinical trial use ONLY".

All study medications will be prepared, packaged and labeled in accordance with the standard operating procedures (SOPs) of the sponsor or its representative, Good Manufacturing Practice (GMP) guidelines, International Council on Harmonization (ICH) Good Clinical Practice (GCP) guidelines and applicable national regulations. All labels on the packaging will comply with local regulations.

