for the last 3 patients who entered the group last, all other patients were cured and discharged. In terms of safety events, with the exception of individual patients who had skin rash or elevated ALT, other adverse events were probably unrelated and no serious adverse events were reported. The adverse reactions in this study were mainly ALT and AST increase, mainly grade 1 adverse reaction, only 1 case of ALT elevation was grade 3 adverse reaction, and the outcome was normalization, and the adverse reactions were common adverse reactions of antiviral drugs. No unexpected adverse reactions occurred. There were no serious adverse events, serious adverse reactions, major adverse events, or death events in the study period.

Recently (2020), the journal NATURE published the article *AZVUDINE (FNC): a* promising clinical candidate for *COVID-19 treatment*⁸, which considers AZVUDINE a promising candidate for the treatment of COVID19, demonstrating its potential in inhibiting viral replication.

[figure not shown]

Figure 4: Mechanism of action of AZVUDINE a) Azvudine nucleoside-based anti-HIV clinical candidate (FNC) for the treatment of COVID-19. Structure of SARS-COV-2 RNA showing a cytosine subunit; b) Diagram showing the RNA replication process of SARS-

COV-2 blocked by FNC; c) Proposed mechanisms of FNC to inhibit SARS-COV-2 activity¹.

To minimize study bias, research participants will be randomized and treatment will be administered blindly, both by research center staff and to participants. The research center's standard treatment will be used to avoid any complications/aggravations of the disease and PLACEBO will be used for masking purposes only.

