5.4. MEASURES TO MINIMIZE STUDY BIAS

5.4.1. Randomization

Research participants, according to eligibility at the time of screening and agreement of the Principal Investigator, will be randomized to one of the two study arms (1:1) by Research-IGZ 1.0 software, generating via the system, random numbers that relate the groups to the volunteers, from the data management plan in **ANNEX 2.**

5.4.2. **Blinding**

A physical report of the blinding will be generated as a security measure and sent to the pharmacist for dispensing the investigational product and to the center coordinator in a sealed envelope. Details about blinding can be found in the Randomization topic in **ANNEX 2.**

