5.4.3. Breaking the emergency blinding

EMERGENCY CEGENE BREAKING can be **INDIVIDUAL** or **TOTAL**, via the system through the administrator password of the Research-IGZ 1.0 software.

Breaking the blinding must be justified by the Principal Investigator, and it is certain that any breaking of blinding will generate Logs in the system, which can be seen in the audit analyses. In case of unblinding, the Principal Investigator and the center coordinator will opt for INDIVIDUAL unblinding. Only in recurring SAEs, suspected of being related to the investigational product, will the FULL blinding be broken.

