6.4. DRUG MANAGEMENT AND RECOVERY

The Principal Investigator, or someone delegated by him/her, must check the following items each time he/she receives the study drugs (investigational drug and PLACEBO): drug name; quantity; package specification; drug lot number; whether it complies with the quality inspection report; expiration date; whether the conditions during transport comply with the storage conditions; check that the outer packaging of the drug is in good condition; whether the package label is clear; check that the drug labels are well attached; etc.

If storage conditions do not meet the specified requirements (airtight at room temperature) during transport, the batch of trial drugs should be stored under the original storage conditions, segregated from other stored products, and reported to the Principal Investigator, who, together with the sponsor, should judge whether the received batch may be used or not.

After the transfer sheet is completed, it must be properly saved and filed in the folder after the trial.

The Principal Investigator, or someone delegated by him/her, must keep accurate and complete records, including the receipt, accounting, dispensing,

administration, retrieval, return, or loss of the investigational drug. The Principal Investigator must ensure that all experimental drugs are used only by the participants in this study, and that dosage and use must be in accordance with the research protocol.

Unused experimental drugs must be returned to the sponsor or disposed of by incineration, according to SMS Ordinance No. 028, dated October 9, 2014, using the Drug Destruction Form, and must not be transferred to any other research participant.

Regardless of the form of disposal, the documentation generated by the chosen process must be archived along with the documents generated during the research so that they can be audited.

Trial medications should be checked on a regular basis. In case of non-compliance events (wrong code, loss, lost medications, damage, signs of loss of quality, etc.), this should be recorded and reported immediately to the Principal Investigator and the sponsor.

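### Arm-specific boxes and serial ranges, plus a drug-name and lot check by the Principal Investigator at receipt, put the blind at risk if those numbers show on bottles that blinded staff handle

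*Protocol*

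**What the plan says.** Section 6.2.2 (Packaging and labeling) states that "Investigational products will be received by the center in separate boxes of AZVUDINE and PLACEBO". The numbering it describes gives each product its own range. It adds a participant label at dispensing, with double checking. "Each bottle with 35 individual tablets will have a label", and the listed contents include "lot number, medication identification number, participant information, care statement, instructions for use and dosage (mg), expiration date".

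Section 6.4 (Drug management and recovery) gives the Principal Investigator or a delegate a list of items to verify "each time he/she receives the study drugs (investigational drug and PLACEBO): drug name; quantity; package specification; drug lot number", and so on.

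On blinding, section 5.1.2 says that "treatment will be administered blindly, both by research center staff and to participants", and section 5.4.4 calls the method double-blind. Section 5.4.2 says that a physical blinding report is "sent to the pharmacist for dispensing the investigational product and to the center coordinator in a sealed envelope", and refers to ANNEX 2 for details. Under section 5.4.3, when a code must be broken the "Principal Investigator and the center coordinator will opt for INDIVIDUAL unblinding"; full unblinding is kept for recurring serious events suspected to be related to the product.

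**The concern.** A kit number protects the blind only if it carries no information about the arm. A scheme with one range per product does carry that information for anyone who can read the number and knows the arm of one bottle. The same holds for a lot number if the two products have different lots.

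The stake is the primary endpoint, a fall of at least one category on the WHO scale by D15. In Table 4, scores 4, 5 and 6 differ by the type of oxygen support, and scores 3 and 4 differ by hospitalisation. Site staff decide on both, and section 9.1 makes discharge depend on the Principal Investigator's evaluation. There is one site (5.1.4), so no other centre would be unaffected by a leak. Knowledge of the arm could bias these decisions, and a leaked allocation cannot be taken back.

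**Working it through.** The protocol states no figure to reproduce. The check sets the sections side by side and follows the consequence.

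**1. What is stated without condition**
- Products arrive in boxes separated by arm (6.2.2).
- The Principal Investigator or a delegate checks drug name and lot number at receipt (6.4). Nothing shown limits this to unblinded staff.
- Each bottle label carries a lot number and a medication identification number (6.2.2).
- Site staff are meant to be blind (5.1.2), and a research team member gives each daily dose (6.2.4).

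**2. What is not stated**
- Whether the box serial is the bottle's medication identification number.
- Whether azvudine and placebo have different lot numbers.
- Whether bottles are renumbered before they reach the ward.

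**3. Consequence if arm-specific serials or lots are readable on dispensed bottles**

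Inputs: 180 participants, 90 per arm (11.1). A full course is 5 tablets × 14 days = 70 tablets, and 70 / 35 per bottle = 2 bottles per participant.

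- *One range per arm.* One code break labels that bottle's range and, by exclusion, the other range. All 180 participants can be classified, which is 180 − 1 = 179 beyond the one intended.
- *One list scrambled over both arms.* One code break gives that participant's arm only. Suppose a reader still splits the numbers into a lower and an upper 90 and labels the halves from the known case. The expected number correct is 1 + 89 × (89/179) + 90 × (90/179) = 1 + 44.25 + 45.25 = 90.5, or 90.5 / 180 = 50.3%, no better than chance.

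This comparison shows what follows from the assumption that the numbers are readable. It is not evidence that they are.

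**4. Route without a code break**

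Whoever checks drug name and lot number at receipt learns which serials, or which lots, belong to which product. Under the same condition, that person could read the arm from a bottle on the ward.

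**5. Can a probability be attached?**

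The protocol gives no expected rate of serious events or of unblinding. For an assumed code-break rate q per participant, the chance of at least one break among 180 is 1 − (1 − q)^180:

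| Assumed q | Chance of at least one break |
|---|---|
| 0.1% | 16% |
| 0.5% | 59% |
| 1% | 84% |
| 2% | 97% |
| 5% | over 99.9% |

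The range is too wide to be informative. It is also the chance of a code break, not of a failed blind, which further requires that blinded staff see the numbers and compare them.

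**The case against.** The strongest reply is that the decisive link is missing from the text. Serials appear only in the sentence about boxes. The label in Figure 6 has blanks for lot number, manufacture date and randomization number, shows no serial field, and uses one wording for both products. The numbering is introduced as an example. Section 5.4.2 gives the blinding report to the dispensing pharmacist, who could receive separated boxes and hand out participant-labelled bottles without unblinding the ward. The tablets look identical (6.2.1), and ANNEX 2 may describe masking of the numbers.

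Much of this stands. A reader might infer that one code break, or even one guessed bottle, reveals every allocation. The documents do not support that: the link from box serial to bottle is not stated, and a guess carries only the certainty of the guess. Nor can a break influence the primary endpoint of participants already past D15. The text also says that products are received in separate boxes, not that they are stored apart.

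The reply does not dispose of the point. A pharmacist who holds the code gives no protection once bottles with range-coded numbers leave the pharmacy. Section 6.4 names the Principal Investigator or a delegate, not the pharmacist, for a check that shows product identity. Figure 6 and the label text in 6.2.2 both put a lot number on the bottle, and 6.4 has that number checked together with the drug name.

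**Conclusion.** The concern holds in conditional form. Sections 6.2.2 and 6.4, as written, do not fit with blinding of site staff (5.1.2) or with individual unblinding as the default (5.4.3). The harm depends on one unresolved fact: whether arm-specific serials or lot numbers are readable on bottles that blinded staff handle. If they are, exposure runs from the one intended participant up to all 180, and receipt alone could be enough. If they are not, a code break stays individual, and what remains is a receipt check that shows product identity to someone who should be blind.

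A reader might go further and conclude that the blind has failed or will probably fail. The documents do not support that. No probability can be derived from them, and the annex with the blinding details is not shown. The point is still more than missing detail, because the protocol describes a supply scheme that is weaker than a standard and cheap alternative.

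**What to change.** - **Section 6.2.2:** replace the arm-specific ranges with one kit-number list randomised across both arms, and use lot labelling that does not reveal the arm. State which number appears on the dispensed bottle.
- **Section 6.4:** limit receipt checks that show product identity to the pharmacist who already receives the blinding report under 5.4.2. The Principal Investigator can keep checks that do not show identity, such as quantity, package condition and transport conditions.
- **ANNEX 2:** confirm that its blinding text agrees with both sections.

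The cost is relabelling or over-labelling of undispensed bottles and a wording change, with no added participants or procedures. Shipping both products mixed in the same boxes is optional.

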6.2.3. Storage and Stability

The shelf life of AZVUDINE and PLACEBO is 2 years. The storage of the experimental medicine and PLACEBO should be at room temperature, in a dark place.

The product proved stable in high temperature and humidity tests at 40°C and 60°C and at 92.5% RH in closed storage and, for up to 30 days, no significant changes were observed in the stability tests of the drug to be used in clinical trials in Brazil. Samples stored open at 75% RH on the 30th day showed moisture absorption of more than 5%.

6.2.4. Dose and method of administration

Research participants will be randomized 1:1 to receive the experimental drug or PLACEBO. Each dose of AZVUDINE or PLACEBO will be administered by the research team member qualified and delegated for this role. The administration, date and time,

will be entered into the study eCRF.

AZVUDINE will be administered orally at a dose of 5mg, once daily, while the participant is hospitalized, for up to 14 days of the full course or until two consecutive negative viral load tests are obtained by RT-PCR.

Research participants will be instructed to swallow the medication whole, without breaking, chewing, crushing, or dividing it before ingesting it. The dose should preferably be given at the same time to all participants every day.

The corresponding PLACEBO will be given in equal amounts, at the same time and respecting the same guidelines described above, to the participants who are allocated to the PLACEBO group.

According to the "Clinical study on the postprandial pharmacokinetics of AZVUDINE" (GQ-FNC-105, Henan Genuine Biotechnology Co, Ltd.), conducted in Beijing You'an Hospital affiliated with Capital Medical University, under the responsibility of [name], in the period from Dec-2015 to May-2018, which is one of the reference of studies related to the preliminary stages of clinical development of AZVUDINE (FNC), the incidence of adverse effects observed in both regimens of experimental drug administration (fasting X postprandial) were similar to each other. All AEs were grade 1 in intensity, requiring no therapeutic management measures, thus demonstrating that the FNC administration regimen does not compromise the safety and tolerability of the investigational drug in healthy subjects.

The experimental drug should be administered daily at 8 pm to minimize the risk of falling, since in preliminary studies, it was observed that vertigo (incidence ≥5%) appears to be an AE likely related to FNC. However, no restrictions on meals.

The total course should not exceed 14 calendar days, even if a dose has been missed. The **lost** investigational product, if it occurs, should follow the principle of "whether the lost medication schedule exceeds 1/2 medication interval or not." If the missed medication schedule is within the first 12 hours of the interval between two medications, the missed investigational product can be re-administered normally and

the next administration can be performed according to the original schedule. If the time of the missed medication is more than the first 12 hours of the two-medication interval, the missed investigational product should not be re-administered and the next administration will be advanced.

If a participant is no longer under hospital care, the administration of AZVUDINE will be discontinued.

6.3. DOSE CHANGES

There are no clinical safety or pharmacokinetic data available for AZVUDINE in patients with renal and/or hepatic impairment. Given the benefit-risk ratio in COVID-19 patients, these participants are excluded from the study.

If the glomerular filtration rate (eGFR) decreases to <25mL/min, administration of the drug should not be given that day. The investigational product can be resumed the next day if the eGFR returns to \geq 30 mL/min. If the participant's renal function worsens to the point of requiring hemodialysis or hemofiltration, administration of the drug should be discontinued.

If ALT and/or AST increase to >5 times above normal, the dose of AZVUDINE should be stopped and not restarted until ALT and AST are ≤5 times the upper limits of normal.

6.3.1. **Overdosage**

AZVUDINE has undergone preclinical studies to identify adverse events related to long-term use of the drug before it is used in patients with HIV (first use of AZVUDINE). In these preclinical tests, long-term exposure to the drug demonstrated that observable adverse events appear when the dose is exceeded by 20-30 times, but because the tests were done for much longer than suggested, AZVUDINE was shown to be safe at doses of 5mg/day, with the maximum dose over 14 days being 70mg in total.

Animal / human equivalent dose	Animal / Administration time	Total dose used in pre-clinical tests over time
3.72mg	1 month	116.6mg
5.60mg	3 months	504.0mg
3.36mg	6.5 months (26 weeks)	655.2mg
3.72mg	9.75 months (39 weeks)	1,088.1mg

Table 7: Relationship between dose and administration time

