 C_{max} in dogs: 85.84-102.55 ng/mL) and 3.099 times lower concentration the dose used in the CHL cell chromosome structure aberration test with the concentration of 7.5 μ g/mL after the 4-hour exposure with or without S9 metabolic activation system.

In this same trial, volunteers receiving 3mg and 4mg of AZVUDINE in a single dose had a plasma exposure of approximately 2.85 and 3.4 ng/mL, respectively. The AUC_{0-t} gradually increased in the 3mg, 4mg and 5mg groups when compared to the 2mg group, with a statistically significant difference between the 4mg and 3mg groups.

Pharmacokinetic data suggest that FNC is rapidly absorbed and slowly eliminated. Total urinary excretion of AZVUDINE increases with increasing dose. Excretion between 0-12h accounted for more than 70% of total excretion in 0-24h.

For the 5 mg dose of AZVUDINE, the average half-life is 13.8h, and it is excreted in the urine in up to 24h.

In the exploratory clinical trials in China, a higher than safety-verified dose (5mg) was used with a dosing regimen of "On Day 1 10mg" in 8 cases at Henan Provincial People's Hospital and yet there were no serious adverse events, serious adverse reactions, major adverse events or death events in the study period. The current dosing design does not use the first dose of 10mg and the current ongoing Phase III clinical trial in China, the dosage is "5mg daily".

In vivo toxicity results from multiple doses of FNC, at high dose in rats (human

equivalent 11.2-56 mg) and dogs (human equivalent 11.16-37.20 mg).

Preclinical trials evaluated much longer administration times than suggested in this clinical trial, leading to a total of the equivalent human dose used in these trials from 116.6 mg (1 month) to 1,088.10 mg (39 weeks).

Animal / human equivalent dose	Animal / Administration time	Total dose used in pre-clinical tests over time
3.72mg	1 month	116.6mg
5.60mg	3 months	504.0mg
3.36mg	6.5 months (26 weeks)	655.2mg
3.72mg	9.75 months (39 weeks)	1,088.1mg

Table 6: Relationship between dose and administration time

The maximum dose of AZVUDINE proposed for this clinical trial is UP TO 70 mg in UP TO 14 DAYS, remembering that the participant can be discharged earlier, reducing the total dose. Long-term exposure to the drug has shown that observable adverse events appear when the dose is exceeded 20-30 times in animals.

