5.2.4. Exclusion Criteria

Individuals with one or more of the following characteristics will not be eligible to participate in this study:

- Patients known or suspected to be sensitive to AZVUDINE or excipients (inactive ingredients: microcrystalline cellulose, lactose hydrate, polyvinylpyrrolidone K30, croscarmellose sodium, magnesium stearate);
- Patients diagnosed with pneumonia caused by other pathogens;
- Patients with liver disease (total bilirubin ≥2mg/dL, ALT/TGP and AST/TGO ≥5 times above normal limit); ¹⁰
- Total neutrophil count <750 cells/L;
- Patients with renal insufficiency (glomerular filtration rate ≤60mL/min/1.73m2) or are receiving continuous renal replacement therapy, hemodialysis, or peritoneal dialysis;
- Patients with congestive heart failure (NYHA grade 3/4), untreated symptomatic arrhythmias, or myocardial infarction within 6 months;

HRH.org 華 人 □

AZVUDINE Clinical Trial Design

- Patients with a history of known liver disease (cirrhosis with ChildPugh classification B and C);
- Individuals with malabsorption syndrome, or other conditions that affect gastrointestinal absorption, and circumstances in which patients need intravenous nutrition, or cannot take medications orally or nasogastrically;
- Women who are pregnant or lactating, or of childbearing potential during the study period and within 6 months after termination of administration;
- Patients already included in other clinical trials;
- Patient under treatment for HIV, Hepatitis C, active Hepatitis B;
- Patients being treated with other antivirals (e.g. lopinavir/ritronavir, remdesivir, umifenovir/arbidol, favipiravir, interferon-α);
- Patients being treated with monoclonal antibodies (e.g. tocilizumab and sarilumab/kevzara);
- Patients who are on a clinical treatment plan that includes concomitant
 administration of any other experimental treatment or off-label use of
 already marketed drugs (e.g. hydroxychloroguine sulfate);
- Patients requiring invasive mechanical ventilation or extracorporeal membrane oxygenation (ECMO) at the time of randomization;
- Any clinically significant medical condition or medical history that, in the investigator's opinion, may discourage participation in the study, such as corrected QT interval >480 on the electrocardiogram, among other conditions.

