9.4. DISCONTINUATION OR INTERRUPTION OF STUDY MEDICATION

If during the course of the study participants develop a more serious condition requiring intubation, considering that the drug is administered orally, the drug will be discontinued.

If during the course of this study participants exhibit any of the following criteria below, the Principal Investigator should judge whether they should discontinue their study medication:

- Confirmed by further examination, TBIL ≥B times the upper limit of normal value, ALT and AST ≥B times the upper limit of normal value;
- If the eGFR decreases to an eGFR <25 mL/min and the participant's renal function worsens to the point of requiring hemodialysis or hemofiltration;
- Any situation that, in the judgment of the Principal Investigator, puts the safety of the participant at risk.

Participants who discontinue study medication early should be encouraged to continue the post-treatment visit to continue safety and efficacy data collection despite discontinuation of study medication. Participants who agree to continue regularly scheduled study visits should complete the study termination assessments (V17) listed in the schedule of procedures detailed in Table 10 as close to the participant's last dose of study medication as possible. The visit data, including the primary reason for discontinuation of study medication, will be recorded in the eCRF. Subsequent study visit data, if applicable, will be recorded in the visit-specific eCRF, and the participant's final study visit will be recorded in the study termination eCRF.

If the reason for participants' discontinuation is an AE, they will continue to receive rigorous medical care until the clear outcome of recovery from AE or steady state. See Section 7 of this protocol for detailed follow-up information. For women who became pregnant during the trial period, the Principal Investigator can refer to item 4.9this protocol for treatment.

Participants discontinuing study medication who are unwilling to continue with regular study visits, but are willing to continue to provide their information for study use will be encouraged to remain in the study. The investigator will contact the sponsor's representative to determine the best approach based on the participant's situation, even if physical and laboratory examinations are not performed, monitoring for drug interactions and adverse events can be considered for such cases.

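### Sections 6.3 and 9.4 disagree on stopping study drug when dialysis is needed: 6.3 directs discontinuation, 9.4 leaves it to the investigator and ties it to eGFR <25 mL/min (minor)

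*Protocol*

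**What the plan says.** Section 6.3 (Dose changes) opens by stating that "There are no clinical safety or pharmacokinetic data available for AZVUDINE in patients with renal and/or hepatic impairment", and gives this as the reason for excluding such patients. It then sets two on-treatment renal rules:

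- eGFR below 25 mL/min: no dose that day; dosing may resume the next day if eGFR has recovered to at least 30 mL/min.
- Need for dialysis: if "renal function worsens to the point of requiring hemodialysis or hemofiltration, administration of the drug should be discontinued".

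Section 9.4 (Discontinuation or interruption of study medication) has two tiers. The first is mandatory and covers one event, a participant "requiring intubation, considering that the drug is administered orally, the drug will be discontinued". The second is a list of criteria for which "the Principal Investigator should judge whether they should discontinue their study medication". The renal entry in that list is: "If the eGFR decreases to an eGFR <25 mL/min and the participant's renal function worsens to the point of requiring hemodialysis or hemofiltration". The list ends with a general entry for anything the investigator considers a risk to the participant's safety.

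Two other places bear on the point. Section 5.2.4 excludes at entry patients with a GFR of 60 or below and those who "are receiving continuous renal replacement therapy, hemodialysis, or peritoneal dialysis". Section 5.1.3 says of the 5 mg dose that "the average half-life is 13.8h, and it is excreted in the urine in up to 24h".

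**The concern.** A site that needs to know whether to stop study drug in a participant who now needs dialysis has two places to look. Section 6.3 tells it to stop. Section 9.4, whose title covers exactly this question, tells it to consider stopping, and only if eGFR is also below 25.

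What is at stake is exposure of a few sick participants to a drug that the protocol describes as excreted in urine, in a condition for which the protocol says it has no safety or pharmacokinetic data and which bars entry to the trial. Section 2.6.1 adds that the doses may overload the renal system. There is also a monitoring consequence. Section 10.8 counts incorrect administration of study medication as a deviation. A dose given on dialysis departs from 6.3 but falls within the discretion of 9.4, so a monitor could not classify it consistently.

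**Working it through.** No formula or planned figure is involved. The check sets the two sections side by side for each clinical state that they cover.

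| State of the participant | Section 6.3 | Section 9.4, as written |
|---|---|---|
| eGFR <25, no dialysis needed | Withhold that day; may restart at eGFR ≥30 | Renal entry not met (both parts needed) |
| eGFR <25 and dialysis needed | Discontinue | Investigator judges whether to discontinue |
| Dialysis needed, recorded eGFR ≥25 | Discontinue | Renal entry not met; only the general safety entry could apply, also by judgement |
| Intubated | Not addressed | Discontinue, no discretion |

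**Row 2 is the substance.** The event is identical, and the instruction is a direction in one section and a discretion in the other. Section 9.4 cannot be read as using 'judge' loosely for a stop, because for intubation it states a stop outright. Dialysis sits on the discretionary side of a distinction that the section itself draws.

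**Row 3 follows from the 'and'.** In 6.3 the need for dialysis is sufficient alone; in 9.4 it is not. This will seldom matter, because a participant who needs dialysis will usually have an eGFR below 25.

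**Does another section settle it?** I found no statement of precedence. Section 9.1 pulls the other way: it says that a need for additional intervention, or a safety endpoint, is not a criterion for withdrawal from trial medication.

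**Does the 6.3 hold close the gap?** Only in part. It is a day-by-day, reversible rule that depends on a current eGFR. Under section 7.3 (visits 3 to 16) drug is given daily while blood is drawn every 48 hours, so at the planned frequency about every second dose has no same-day value behind it.

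**How many could be affected?** The documents give no rate, and I assume none. The group is bounded by:

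- entry GFR above 60 (section 5.2.4). Reading the entry and on-treatment limits on the same scale, reaching an eGFR below 25 means a fall of more than 60 − 25 = 35 mL/min, or more than 35/60 = 58% of the entry value;
- a course of at most 14 days;
- intubated participants already removed by the mandatory stop.

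**The case against.** The strongest reply is that the two sections can both be obeyed. Section 6.3 says 'should', not 'must'. Nothing in 9.4 directs continued dosing, and an investigator who meets the 9.4 criterion and stops has satisfied both. Section 12.8 makes the investigator responsible for compliance with the protocol as a whole, and the general safety entry in 9.4 catches whatever the renal entry misses. On this view one section is only worded more loosely than the other.

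Much of that stands. It is why I say that 6.3 directs discontinuation rather than requires it, and why the point is minor. It does not remove the inconsistency: 6.3 leaves no room for judgement on dialysis, and both the renal and the general entries in 9.4 consist of judgement. A stopping rule should read the same wherever a site finds it.

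Three stronger readings are tempting and not supported:

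- A reader might infer that the protocol authorises dosing on dialysis. It does not. That result arises only if a site applies 9.4 without 6.3.
- A reader might infer a matching contradiction in the liver rules, because the exclusion reads "Patients with liver disease (total bilirubin ≥2mg/dL, ALT/TGP and AST/TGO ≥5 times above normal limit" while the 6.3 hold uses 'and/or' for the two enzymes. The documents do not establish this. One is an entry criterion and the other an on-treatment hold, so they need not match, and the exclusion reads naturally as a list of separate limits.
- A reader might infer harm to the primary comparison. Nothing in the documents supports that, and none is claimed.

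**Conclusion.** The inconsistency is real and visible in the current text: for a participant who needs hemodialysis or hemofiltration, 6.3 directs that study drug be discontinued, while 9.4 merges that event with eGFR below 25 and leaves it to the investigator. The directed-versus-discretionary difference carries the point; the 'and' is a lesser defect.

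It is minor. It will rarely be triggered, most investigators would probably stop the drug anyway, and it has no effect on sample size, endpoints or the primary analysis. The conclusion rests on the protocol text alone. It assumes that no annex (none is reproduced) states which section takes precedence.

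**What to change.** In section 9.4:

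1. Delete the combined renal bullet from the list left to the investigator's judgement.
2. Beside intubation, state that need for hemodialysis or hemofiltration, whatever the eGFR, is a mandatory discontinuation of study drug, with a reference to 6.3.
3. State that an eGFR below 25 mL/min without dialysis is handled by the 6.3 rule (same-day hold, restart at 30 mL/min or above).

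Step 3 is needed. If only the dialysis half were moved, eGFR below 25 would remain in 9.4 as a stand-alone discontinuation trigger at odds with the same-day hold in 6.3.

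The cost is a short protocol amendment with documented ethics and regulatory approval (section 10.9), including written approval from ANVISA (section 12.1). It changes no eligibility criterion, endpoint, sample size or analysis, and can be submitted with the next amendment. The liver exclusion should be left as it is: changing eligibility after recruitment has begun is not justified by this point.
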